### **Protocol Summary**

#### Study center

The First Affiliated Hospital of Soochow University

# Methodology

A phase III, open-label, single-center, randomized placebocontrolled trial

#### **Primary objective**

The primary outcome was the incidence of transplant-associated thrombotic microangiopathy (TA-TMA).

#### Inclusion criteria

Patients with malignancies between the ages of 12 and 70 who are scheduled to undergo allogeneic hematopoietic stem cell transplantation are eligible to enter the study.

Eligible patients met the following criteria. (i) planned to receive allo-HSCT; (ii) established stable donor hematopoiesis; (iii) Eastern Cooperative Oncology Group (ECOG) performance status of 0-2.

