#### Intervention

Patients were randomized 1:1 by interactive response technique to receive either oral NAC (50 mg/kg/day continuously from 9 days before HSCT to 30 days after HSCT) or a placebo. A placebo (identical-looking tablets) was administered similarly to NAC for patients randomized to the placebo group.

Total number of patients: 300

Total duration of the study: 3 years

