#### Dosage and administration

Patients were randomized 1:1 by interactive response technique to receive either oral NAC (50 mg/kg/day continuously from 9 days before HSCT to 30 days after HSCT) or a placebo. A placebo (identical-looking tablets) was administered similarly to NAC for patients randomized to the placebo group.

Drug: N-Acetylcysteine

50mg/Kg.d, oral

Other Name: NAC

Drug: Placebo Oral Tablet

50mg/Kg.d, oral

Other Name: Placebo

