#### Statistical methods

Kaplan-Meier survival analysis was used to estimate cumulative incidence of TA-TMA, the cumulative predicted overall survival (OS) rate and event-free survival (EFS) rate, cumulative recurrence rate of malignant hematologic disease, cumulative mortality associated with transplantation, and log-rank test was performed. The statistical process and graph were all run on SPSS 13.0 software. All tests were bilateral, and P≤0.05 was considered to be significant. OS and EFS are estimated by Kaplan-Meier method.

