#### Withdrawal from the study

The main withdrawal criteria are as following:

- ➤ Changes in the patient's condition after inclusion, which suggests that the study protocol is unsuitable for the patient;
- Severe complications affecting the implementation of the study treatment;
- ➤ Patients who are confirmed to require emergency treatment due to other diseases after inclusion;
- >Treatment unmated with the study protocol;
- ➤ Patients who voluntarily quit or discontinue any examination, treatment and monitoring required by the study for personal reasons at any stage after inclusion in this study. The PI also has the right to withdraw patients from the study if he/she feels that the withdrawal is in the best interests of the patients.

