# Responsibility of investigator

The responsibilities of investigators are as follows:

- ➤Investigators, participated in the clinical trial, should be obtained certificate for assistant practicing doctor, resigned and attended the training of the GCP guidelines and the correlation of laws and regulations, possessed specialty, qualification and ability in clinical trial.
- ➤ Subjects are adequately recruited by the investigator during required time according to the clinical trial, and

operation capacity and possibility to be qualified the item should be evaluated by the previous working experience.

Investigators are familiar with clinical trial protocols and execute instruction strictly according to the protocols and case report form.

➤ In all adverse events, subjects must be taken appropriate therapies and made a contact with the investigator as soon as possible. Investigators will take responsibilities of relevant medical decision of clinical trial to ensure subjects that is taken adequate medical treatment.

Any information on the case report form possesses original data, to ensure the case history and case report form filled in truly, accurately, completely, timely, regularly and legally.

Subjects will be illustrated the relevant situation where the clinical trial is fully consent by Ethics Committee. The informed consent will be acquired and, during the process, it must meet the specification.

Supervision and inspection will be received by supervisor and inspector assigned by sponsor to ensure the quality of clinical trial.

Any advices and suggestions focused on the study protocols might be submit to the principal institution of clinical research, and made a discussion with sponsors to decide whether adopting the above advice or suggestions, during the clinical trial.

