### Organization and responsibility

The Research Committee is responsible for developing study protocol, auditing patient eligibility and guiding interpretation of informed consent. It is also responsible for collection of complication reports, guiding diagnosis and treatment of complications and emergency intervention for serious complications, as well as approving the content and distribution of all publications related to the study.

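### The donor-hematopoiesis inclusion criterion cannot be assessed before the planned transplant; enforced later, it excludes patients after randomisation

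*Combined protocol and SAP*

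**What the plan says.** The Inclusion criteria section opens with patients "scheduled to undergo allogeneic hematopoietic stem cell transplantation are eligible to enter the study", so the transplant lies in the future at entry. It then lists what eligible patients must meet, including "i) planned to receive allo-HSCT; (ii) established stable donor hematopoiesis". The criteria are listed together, with nothing to suggest that they are alternatives.

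The Intervention section randomises 1:1 to "oral NAC (50 mg/kg/day continuously from 9 days before HSCT to 30 days after HSCT) or a placebo", with placebo given in the same way, and sets the total at 300. Dosage and administration repeats the schedule: "continuously from 9 days before HSCT to 30 days after HSCT".

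Stable donor hematopoiesis is not defined, has no assessment time, and is not linked to any earlier transplant. Statistical methods states that "OS and EFS are estimated by Kaplan-Meier method" and uses the same approach for TA-TMA incidence, but gives no analysis set and no time origin. Withdrawal from the study allows withdrawal for a change in the patient's "condition after inclusion, which suggests that the study protocol is unsuitable for the patient"; graft failure is not named. Investigators are to "execute instruction strictly according to the protocols and case report form" (Responsibility of investigator), and the Research Committee is charged with "auditing patient eligibility and guiding interpretation of informed consent" (Organization and responsibility).

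**The concern.** An eligibility criterion should be answerable from what is known at randomisation. Read for the planned transplant, criterion (ii) is not: it describes a result of the procedure the patient is still waiting for.

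If the criterion is enforced once engraftment is known, patients who die early or never engraft leave the primary and survival analyses, together with any TA-TMA they had. Patients who develop TA-TMA and later engraft stay in. The analysis then compares patients selected on an event that occurs during or after study treatment, and the protection of randomisation is lost. The comparison between arms is biased if such losses differ by arm or are affected by treatment.

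Two features add to the exposure. Without a defined analysis set, two analysts could follow the text and analyse different populations, one all randomised and the other engrafted only. And the Methodology section calls the trial open-label although the Intervention section describes an identical-looking placebo; if allocation is known, an undefined judgement of stability could be influenced by arm.

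**Working it through.** **Sequence of events**

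1. Study drug starts on day -9 (Intervention; Dosage and administration).
2. Allocation must precede the first dose, so randomisation is on day -9 or earlier.
3. Donor cells are infused on day 0, so donor hematopoiesis from that graft cannot exist until after day 0.
4. Criterion (ii) can therefore be assessed only more than 9 days after the latest possible randomisation.

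Dosing runs from day -9 to day +30, which is 30 + 9 + 1 = 40 days counting day 0. Days -9 to -1 are 9 of these, 9/40 = 22.5%. This shows only how much randomised treatment precedes the graft; it does not measure bias.

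**Other readings**

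- *Engraftment from an earlier transplant.* This could be assessed at baseline, but it would restrict a 300-patient trial to repeat transplants. The documents mention no earlier transplant.
- *Randomisation after engraftment.* This is ruled out by the day -9 start.
- *Drafting error.* This is plausible, but nothing in the text corrects it.

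**Illustration of size.** Only the 300 patients (150 per arm at 1:1) and the two-sided 5% level come from the documents. There is no plan figure to reproduce, because no event rate, effect size or dropout rate is given. Every rate below is assumed.

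Let P be the true TA-TMA incidence in an arm, L the proportion lost, and R the risk in lost relative to kept patients.

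- Patients lost: 5% to 10% of 300 = 15 to 30.
- TA-TMA cases lost if R = 1: 15 × 0.10 = 1.5 to 30 × 0.20 = 6.
- Incidence in kept patients: P / [(1 − L) + L·R]. Cases lost per arm: 150 × L × R × kept incidence.
- R = 3, P = 10%, L = 5%: kept incidence 0.10/1.10 = 9.09%; lost 150 × 0.05 × 3 × 0.0909 = 2.05 per arm, 4.1 in total.
- R = 3, P = 20%, L = 10%: kept incidence 0.20/1.20 = 16.67%; lost 150 × 0.10 × 3 × 0.1667 = 7.5 per arm, 15.0 in total.

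Type I error uses a two-sided pooled z-test: Φ[(d − 1.96·s0)/s1] + Φ[(−d − 1.96·s0)/s1], where d is the difference in kept incidence and s0 and s1 are the pooled and unpooled standard errors. With R = 3 and no true effect:

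| Loss by arm | Patients kept | Kept incidence, P = 10% | Kept incidence, P = 20% | Risk ratio | Type I error (P = 10%, 20%) |
|---|---|---|---|---|---|
| Equal | equal | equal | equal | 1.00 | 5.0%, 5.0% |
| 5% vs 10% | 142.5 vs 135 | 9.09% vs 8.33% | 18.18% vs 16.67% | 1.10/1.20 = 0.917 | 5.55%, 6.25% |
| 5% vs 15% | 142.5 vs 127.5 | 9.09% vs 7.69% | 18.18% vs 15.38% | 1.10/1.30 = 0.846 | 6.87%, 9.29% |

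For mortality M, if every lost patient dies, kept mortality is (M − L)/(1 − L). For M = 20% this gives 15.8% (L = 5%) and 11.1% (L = 10%); for M = 30%, 26.3% and 22.2%. Reported mortality would be 3.7 to 8.9 percentage points too low, if survival is meant to run from randomisation.

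**The case against.** The strongest reply is that the harm is hypothetical. Nothing says that patients without engraftment are dropped, graft failure is not a named withdrawal reason, and the duties to follow the protocol and audit eligibility are general ones that do not mention rechecking eligibility after entry. The neighbouring text also contains a visible slip, since the Exclusion criteria list the absence of uncontrolled infection as a reason to exclude. A drafting error, cured by one corrected line, is therefore quite possible. Nor are criteria (i) and (ii) logically incompatible: a patient with an earlier donor graft could meet both.

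The illustration is also open to challenge. All its rates are assumed and equal loss causes no inflation. It uses a test of proportions where Statistical methods plans a log-rank test, and it takes lost patients to be at equal or higher risk. Patients who die early have less time to develop TA-TMA; with R = 0.5 and 5% vs 10% loss the ratio is 0.975/0.95 = 1.03, in the other direction.

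These points limit what can be said about size and direction. They do not remove the contradiction: no reading supported by the text makes criterion (ii) assessable at randomisation for the planned transplant. A stated eligibility rule cannot be left for investigators and auditors to ignore silently. The missing analysis set and time origin would be gaps in any case; they belong here because nothing else in the plan prevents an engrafted-only analysis.

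**Conclusion.** The concern holds and must be fixed. Confidence is high that criterion (ii) conflicts with enrolment before transplant and with the day -9 start of study drug; this follows from the order of events and needs no assumption. The consequence for the results is conditional: it arises only if the criterion is enforced for the planned transplant, and the documents do not show that it was.

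The size of any bias cannot be computed from the documents. On the assumed inputs it runs from no inflation with equal loss to a type I error of about 9.3%, which needs 5% vs 15% loss, three-fold risk in lost patients and 20% incidence together. The direction depends on which arm loses more patients and on their risk. The conclusion does not rest on these figures.

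**What to change.** Reconcile the Inclusion criteria with Intervention and with Dosage and administration:

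- Take criterion (ii) out of eligibility, so that entry depends only on information available before randomisation. If an earlier transplant was meant, say so explicitly.
- In Statistical methods, state that the primary analysis includes all randomised patients in their allocated arm, timed from randomisation, whether or not they engraft.
- Define engraftment and graft failure and record them as post-baseline outcomes. Label any engrafted-only analysis as supportive.
- If any randomised patient has already been removed under criterion (ii), list these patients by arm and restore them to the analysis.

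The cost is an amendment to one criterion, a statement of analysis set and time origin, and one defined item on the case report form. No extra patients are needed. Because early deaths and graft failures would count, reported survival may be slightly less favourable.

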#### Intervention

Patients were randomized 1:1 by interactive response technique to receive either oral NAC (50 mg/kg/day continuously from 9 days before HSCT to 30 days after HSCT) or a placebo. A placebo (identical-looking tablets) was administered similarly to NAC for patients randomized to the placebo group.

Total number of patients: 300

Total duration of the study: 3 years

#### **Background**

Transplant-associated thrombotic microangiopathy (TA-TMA) is a severe complication in patients following hematopoietic stem cell transplantation (HSCT). Previous investigations suggest that multiple factors resulting in endothelial cell injury lead to the occurrence of TA-TMA. Specifically, the abnormity of complement system contributes to the development of TA-TMA. TA-TMA shares a similar clinical manifestation with thrombotic thrombocytopenic purpura (TTP) and atypical hemolytic uremic syndrome (aHUS), which is characteristic with microangiopathic hemolytic anemia, platelet consumption, fibrin deposition in the microcirculation, and, ultimately, endorgan injury [1]. However, the diagnostic criteria of TA-TMA are far from accurate. Although several diagnostic criteria

had been proposed, no criterion has been rigorously evaluated clinically due to lack of pathological diagnosis. Moreover, the pathogenesis of TA-TMA is still unclear. Conventional treatment management is less efficient [2]. Plasma infusions or therapeutic plasma exchange is considered as limited efficacy, with relatively low response rates (20–50%) in comparison to idiopathic TTP (75%) generally reported [3].

N-acetylcysteine (NAC) is an antioxidant synthesized from cysteine that increases glutathione biosynthesis and scavenges reactive oxygen species directly or indirectly [4]. NAC was recently suggested as a potential treatment for patients with thrombotic thrombocytopenic purpura (TTP) [5-7]. Li and colleagues provide a case report of a TTP patient relieved with NAC, providing the first clinical evidence for the efficacy of NAC in treating TTP [5]. In our study, we explored whether TA-TMA patients might benefit from NAC via targeting complement.

#### **Study Outcomes**

#### **Primary Outcome:**

The primary outcome was the incidence of TA-TMA.

### **Secondary Outcome Measures:**

- 1. The level of VWF multimers in patients post HSCT.
- 2. The level of endothelial micro particle in patients post HSCT.
- 3. The level of TNF- $\alpha$  in patients post HSCT.
- 4. The level of ROS in patients post HSCT.

#### Dosage and administration

Patients were randomized 1:1 by interactive response technique to receive either oral NAC (50 mg/kg/day continuously from 9 days before HSCT to 30 days after HSCT) or a placebo. A placebo (identical-looking tablets) was administered similarly to NAC for patients randomized to the placebo group.

Drug: N-Acetylcysteine

50mg/Kg.d, oral

Other Name: NAC

Drug: Placebo Oral Tablet

50mg/Kg.d, oral

Other Name: Placebo

#### Statistical methods

Kaplan-Meier survival analysis was used to estimate cumulative incidence of TA-TMA, the cumulative predicted overall survival (OS) rate and event-free survival (EFS) rate, cumulative recurrence rate of malignant hematologic disease, cumulative mortality associated with transplantation, and log-rank test was performed. The statistical process and graph were all run on SPSS 13.0 software. All tests were bilateral, and P≤0.05 was considered to be significant. OS and EFS are estimated by Kaplan-Meier method.

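### Kaplan-Meier is named for the cumulative incidence of TA-TMA, relapse and transplant mortality with no competing event, so the reported percentages are too high once target events follow competing ones

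*Combined protocol and SAP*

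**What the plan says.** The Primary Outcome section reads "The primary outcome was the incidence of TA-TMA". It gives no time horizon. The Statistical methods section then fixes the estimator: "Kaplan-Meier survival analysis was used to estimate cumulative incidence of TA-TMA". The same sentence extends it, after OS and EFS, to "cumulative recurrence rate of malignant hematologic disease, cumulative mortality associated with transplantation, and log-rank test was performed". The significance rule is "All tests were bilateral, and P≤0.05 was considered to be significant".

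No section names a competing event, says how a death without TA-TMA is handled, or mentions another estimator of incidence. Relapse and transplant-associated mortality appear only in Statistical methods, not in the lists of primary and secondary outcomes.

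**The concern.** The population is "Patients with malignancies between the ages of 12 and 70 who are scheduled to undergo allogeneic hematopoietic stem cell transplantation". Deaths and relapses are expected in such patients, and the plan itself analyses both. A patient who dies without TA-TMA can no longer develop it. Kaplan-Meier, with death treated as censoring, gives that patient the same future risk as those still alive. The result estimates what would happen if nobody died first, not the proportion of patients who develop TA-TMA.

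The competing event differs by endpoint:

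- **TA-TMA:** death without TA-TMA. Relapse does not in itself prevent TA-TMA, so it matters here only if patients are censored at relapse.
- **Relapse:** death without relapse.
- **Transplant-associated mortality:** relapse, and death from other causes if these are counted separately.

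The primary outcome is worded as an incidence, so readers will use the percentage in each arm and the absolute difference. If competing mortality is similar in both arms, the ratio hardly moves. If it differs, part of an apparent difference in these percentages can be created or hidden. More patients would not remove the bias.

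**Working it through.** **Inputs.** From the documents: 300 patients ("Total number of patients: 300") and 1:1 allocation ("Patients were randomized 1:1 by interactive response technique"), so about 150 per arm. They give no TA-TMA rate, death rate or horizon, and no incidence figure to reproduce. All rates below are assumptions.

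**Formula.** Let F1 be the true cumulative incidence of the target event and F2 that of the competing event, both at the horizon. With constant cause-specific hazards:

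- total cumulative hazard H = −ln(1 − F1 − F2)
- target hazard H1 = H × F1/(F1 + F2)
- Kaplan-Meier figure = 1 − exp(−H1)

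Example with F1 = 0.15 and F2 = 0.10: H = −ln(0.75) = 0.2877; H1 = 0.2877 × 0.6 = 0.1726; 1 − exp(−0.1726) = 0.1585.

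**Limits set by the order of events.** If all TA-TMA comes before any competing death, there is no bias. If all competing deaths come first, the figure is F1/(1 − F2). For example, 20 of 100 patients die first and 15 of the remaining 80 develop TA-TMA: 15/80 = 18.8%.

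**One arm, true TA-TMA incidence 15%:**

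| Competing deaths | Kaplan-Meier figure, constant hazards | Relative excess | All deaths first (upper limit) |
|---|---|---|---|
| 5% | 15.4% | 3% | 15.8% |
| 10% | 15.9% | 6% | 16.7% |
| 20% | 16.9% | 12% | 18.8% |
| 30% | 18.1% | 20% | 21.4% |

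A simulation of 200,000 patients with 15% TA-TMA and 20% competing deaths gave 16.9% by Kaplan-Meier and 15.0% by the cumulative incidence function.

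**Two arms** (constant hazards; differences from unrounded values):

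| True TA-TMA | Competing deaths | Kaplan-Meier figures | True difference | Reported difference |
|---|---|---|---|---|
| 15% v 7.5% | 10% v 10% | 15.85% v 7.91% | 7.5 points | 7.9 points (ratio 2.00) |
| 15% v 7.5% | 20% v 10% | 16.86% v 7.91% | 7.5 points | 8.9 points |
| 15% v 15% | 10% v 25% | 15.85% v 17.43% | 0 | 1.6 points, reversed in sign |

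For scale, the standard error of a difference at 15% with 150 per arm is √(2 × 0.15 × 0.85/150) = 0.041, or 4.1 points.

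**Relapse and transplant mortality.** The documents do not define EFS. If it counts only these two events, their true incidences must add up to 1 − EFS. By Kaplan-Meier they do not:

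- True 15% and 10% give 15.9% and 10.9%: sum 26.7% against 25%.
- True 25% and 20% give 28.3% and 23.3%: sum 51.6% against 45%.

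**The case against.** The strongest reply is that the error may be small and leaves the planned test intact. If TA-TMA occurs early and deaths come later, the bias approaches zero. At 5% to 10% competing deaths the excess on a true 15% is 0.4 to 0.9 points. The false difference of 1.6 points needs quite unequal mortality (10% against 25%) and is about 0.4 of the standard error (1.6/4.1). Nothing in the documents supports one set of rates over another. Censoring at death is also an inference, since the plan states no rule.

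Much of this stands as a limit on size. It does not rescue the estimator: the bias can only go upwards, and it falls on the primary percentages. Censoring at death is ordinary Kaplan-Meier practice, and silence on the rule is part of the problem.

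A second reply is that a cumulative incidence estimate and a log-rank test answer different questions. That is true. In the example with equal incidences of 15%, the TA-TMA cumulative hazards are 0.173 and 0.192, a ratio of about 1.11, so the log-rank test is not under its null although the incidences are equal. The pairing is standard, but the report must label the log-rank test as a comparison of cause-specific hazards. Gray's test can be shown beside it.

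Third, time from randomisation needs a clear date of randomisation. Eligibility requires established donor haematopoiesis, yet dosing starts 9 days before HSCT. Those sections must be reconciled in any case.

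**Conclusion.** The concern holds. As written, the plan yields percentages for TA-TMA, relapse and transplant mortality that are never too low, and are too high whenever target events follow competing ones. Under constant hazards and a true TA-TMA incidence of 15%, the excess runs from 0.4 points at 5% competing deaths to 3.1 points at 30%. The order of events moves it between zero and 6.4 points (21.4 − 15) at 30%. These sizes rest on assumed rates and on censoring at death; the direction does not depend on the rates.

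The fault lies in the reported percentages and their difference. The log-rank p-value stands as a test of the cause-specific hazard, and Kaplan-Meier is correct for OS and EFS. The point should be fixed, most of all for the primary outcome.

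**What to change.** Replace the incidence part of Statistical methods with wording such as:

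> The cumulative incidence of TA-TMA (competing event: death without TA-TMA), of relapse (competing event: death without relapse) and of transplant-associated mortality (competing events: relapse, and death from any other cause if counted separately) is estimated from randomisation by the Aalen-Johansen cumulative incidence function. It is reported per arm, with the difference and its 95% confidence interval, at day [X]. Patients are censored only at last contact; stopping study treatment is not in itself a censoring event.

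The trial team must set X. The documents give no horizon; they say only that treatment runs from 9 days before to 30 days after HSCT. Keep the log-rank test, labelled as the comparison of cause-specific hazards, with Gray's test alongside if wished. Keep Kaplan-Meier for OS and EFS. Use software that provides the cumulative incidence function.

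The cost is small: a change of SAP wording and a software routine, with no change to sample size. Dates of death and relapse are needed, and the planned OS and recurrence analyses already require them. One point must be confirmed: withdrawal is allowed for reasons such as "Severe complications affecting the implementation of the study treatment", and no section describes follow-up after withdrawal. Reported incidences will be the same or somewhat lower.
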